8.4 Routine Adverse Event Reporting

All Adverse Events **must** be reported in routine study data submissions. **ALL AEs are to be reported through ONCORE.**

8.5 Secondary Malignancy

A *secondary malignancy* is a cancer caused by treatment for a previous malignancy (e.g., treatment with investigational agent/intervention, radiation or chemotherapy). A secondary malignancy is not considered a metastasis of the initial neoplasm.

All secondary malignancies that occur following treatment with an agent under an IND/IDE must be reported through **ONCORE**. Three options are available to describe the event:

- Leukemia secondary to oncology chemotherapy (e.g., acute myelocytic leukemia [AML])
- Myelodysplastic syndrome (MDS)
- Treatment-related secondary malignancy

Any malignancy possibly related to cancer treatment (including AML/MDS) should also be reported via the routine reporting mechanisms outlined in each protocol.

8.6 Second Malignancy

A second malignancy is one unrelated to the treatment of a prior malignancy (and is **NOT** a metastasis from the initial malignancy).

A list of the adverse events and potential risks associated with the investigational or commercial agents administered in this study can be found in investigator's brochure.

9. LABELING, PACKAGING, STORAGE AND RETURN OF CLINICAL SUPPLIES

9.1 Investigational Product

9.1.1 Nivolumab

The investigator shall take responsibility for and shall take all steps to maintain appropriate records and ensure appropriate supply, storage, handling, distribution and usage of investigational product in accordance with the protocol and any applicable laws and regulations. Clinical Supplies will be provided by BMS as summarized in Table X.

Clinical Supplies will be provided by BMS.

9.1.2 Metformin ER

Metformin will be bought by the investigational pharmacy services at Winship Cancer Institute and the funding will be provided by BMS.

The investigator shall take responsibility for and shall take all steps to maintain appropriate records and ensure appropriate supply, storage, handling, distribution and usage of investigational product in accordance with the protocol and any applicable laws and regulations.

9.1.3 Packaging and Labeling Information

Clinical supplies will be affixed with a clinical label in accordance with regulatory requirements.

9.1.4 Clinical Supplies Disclosure

This trial is open-label; therefore, the subject, the trial site personnel, the Sponsor-investigator and/or designee are not blinded to treatment. Drug identity (name, strength) is included in the label text; random code/disclosure envelopes or lists are not provided.

9.1.5 Storage and Handling Requirements

Clinical supplies must be stored in a secure, limited-access location under the storage conditions specified on the label.

Receipt and dispensing of trial medication must be recorded by an authorized person at the trial site.

Clinical supplies may not be used for any purpose other than that stated in the protocol.

9.1.6 Returns and Reconciliation

The investigator is responsible for keeping accurate records of the clinical supplies received from BMS or designee, the amount dispensed to and returned by the subjects and the amount remaining at the conclusion of the trial. Upon completion or termination of the study, all unused and/or partially used investigational product will be destroyed at the site per institutional policy. It is the Investigator's responsibility to arrange for disposal of all empty containers, provided that procedures for proper disposal have been established according to applicable federal, state, local and institutional guidelines and procedures, and provided that appropriate records of disposal are kept.

10. STATISTICAL CONSIDERATIONS

10.1 Study Design/Endpoints/ Determination of Sample Size

This is a phase II trial. Primary objective is to determine the overall response rate. Historically ORR with single agent Nivolumab in CRC is <5% and Metformin and Nivolumab combination will have ORR of 15%. Simon's MinMax two stage design is employed for the study with power of 80% and alpha of 0.1. If there is 1 response in first 18 patients in the first stage of the study, then it will proceed with second stage to enroll total of 28 patients. If there are 3 or more responders out of the 28 patients then it would be positive study. This will enable us to evaluate clinical endpoints (ORR, CEA, RFS, OS) as well as evaluate the impact on immune biomarkers.

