Nivolumab will be provided intravenously and metformin will be provided in tablet form. Eligible subjects will receive nivolumab 480 mg IV every 4 weeks and metformin 1000 mg po BID according to the study design.

Control therapy, dose and administration: N/A

Efficacy evaluation/Endpoints:

Primary Endpoint: ORR

Secondary Endpoints: To determine PFS, OS, and biochemical response (CEA), immune and metabolic biomarkers in tumor microenvironment and systemic circulation (pre and post research biopsy required)

Safety evaluation/Endpoints:

[figure not shown]
NCI Common Toxicity Criteria Version 4.0

Rationale for number of subjects: Primary objective is to determine the overall response rate. Historically ORR with single agent nivolumab in CRC is <5% and metformin and nivolumab combination will have ORR of 15%. Simon's MinMax two stage design is employed for the study with power of 80% and alpha of 0.1. If there is 1 response in first 18 patients in the first stage of the study, then it will proceed with second stage to enroll total of 28 patients. If there are 3 or more responders out of the 28 patients then it would be positive study. This will enable us to evaluate clinical endpoints (ORR, CEA, RFS, OS) as well as evaluate the impact on immune biomarkers.

Statistical methods: Phase II design

Translational Research: Correlative assays will include- immune profiling of TILs and circulating lymphocytes, plasma cytokine levels, and key metabolic biomarkers of relevance to mechanism of metformin action when administered in combination with immunotherapy. Paired biopsies will be obtained in all patients.

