4. BACKGROUND AND RATIONALE

4.1 *Study Disease*

Colorectal cancer (CRC) is the third most common cancer in the US and it is estimated to cause more than 50,000 deaths in 2018. [1] Approximately 20% of patients have metastatic CRC at initial presentation who have a 5 year overall survival of 14%. [1] Clear majority of the CRCs develop through chromosomal instability (CIN) pathway and approximately 15% develop from the microsatellite instability (MSI) pathway which results from deficient DNA mismatch repair (MMR). [2] While about 15% of all CRCs are MSI-H, about 4% of metastatic CRCs are MSI-H. [3] Germline mutations in MMR genes such as MLH1, MSH2, MSH6, PMS2 or epigenetic inactivation of MLH1 gene cause deficient MMR. MSI-H CRCs have better stage adjusted prognosis compared to MSS CRCs. [2] Consensus molecular subtype (CMSs) system classifies CRCs into 4 different gene expression-based molecular subtypes: CMS1 (14%, microsatellite unstable with strong immune activation and hypermutated), CMS2 (canonical, 37%, epithelial differentiation, strong WNT and MYC Signaling activation), CMS3 (13%, characterized with metabolic dysregulation and KRAS mutations) and CMS4 (mesenchymal, 23%, phenotype with strong transforming growth factor beta activation, stromal invasion and angiogenesis), an unclassified group with mixed features represent 13% of remaining cases. [4] The immunological signatures of tumor microenvironment (TME) and the molecular subtypes were shown to be correlated. [Becht et al] CMS1 is the most immunogenic subtype of all four subtypes while the CMS4 is the second most immunogenic. [4, 5] Immunotherapy with checkpoint inhibitors has been proven to be very effective in the treatment of metastatic CRC with high level of Microsatellite Instability (MSI-H), but ineffective in Microsatellite Stable (MSS) CRC. [6] Immunotherapy with anti-PD-1 agents is approved only in MSI-H metastatic CRC patients after failure of standard first line systemic chemotherapy. [7] MSI-H tumors respond to check point inhibitors because of high mutational rate, up 20 times higher compared to MSS CRC, as well as significant immune checkpoint expression [5]. At the present time patients with MSI-H status, high expression of neo-antigens and TILs are good candidates for check point inhibition whereas MSS CRC patients lack response to immunotherapy due to opposite tumor features. [5] TME is essential for prognosis and is a viable target for anti-cancer therapy by modulation of the TME composition. Only a small set (4%) of metastatic CRCs would be candidate for anti-PD-1 therapy therefore there is significant unmet need for innovative approaches to combine anti-PD1 therapy with other agents to achieve manipulation of TME of CRCs and sensitize MSS CRCs to anti-PD-1 therapy. For example, by modulating the tumor microenvironment antitumor responses (ORR 17%, 4PR, 5SD) were reported in MSS patients when a checkpoint inhibitor was combined with Cobimetinib in a phase Ib trial based on preclinical data showing increased intratumoral CD8+ T cell infiltration and increased sensitivity to PDL-1 inhibition. [8] The preclinical rationale was also confirmed in this phase Ib trial by showing increased CD8+ T cell infiltration, MHC-I expression and PDL-1 upregulation in serial tumor biopsies on treatment.

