
4.2 *Investigational Agents*

4.2.1

Nivolumab in CRC:

Immune checkpoint expression as programmed death 1 (PD-1) or cytotoxic T-lymphocyte-associated antigen (CTLA-4) by tumor cells is one of the major immune evasion mechanisms. [3, 9] PD-1, a member of B7/CD28 costimulatory receptor family, down regulates T-cell activation by binding to its receptors programmed death ligand 1 (PD-L1) and programmed death ligand 2 (PDL-2). Nivolumab is a fully humanized monoclonal IgG4 anti-PD-1 inhibitor which is currently approved for MSI-H CRC after progression on systemic chemotherapy.

Nivolumab was studied as a single agent at doses of 0.3-10 mg/kg in the first phase I study in 39 patients with advanced solid tumors, 1/14 CRC patients achieved durable complete response (CR), no maximum tolerated dose was determined. [10] That patient had MSI-H positive CRC. In the following phase Ib study with single agent Nivolumab at a dose of 0.1-10 mg/kg IV in 296 patients with treatment refractory solid tumors none of the 19 CRC patients had objective response. Of note these patients included predominantly MSS CRCs. [11]

CheckMate 142 Phase II study of single agent Nivolumab 3 mg/kg IV every 2 weeks in 74 treatment refractory MSI-H CRC patients revealed 31.1% objective response rate (ORR), 3% complete response (CR) and 69% disease control rate (DCR) for 12 weeks or longer at a median follow up of 12 months. [12] More updated results of the same study at median follow up of 21 months revealed 34% ORR, 9% CR, and 62% DCR. [13] The response rates did not differ between Tumor expression of PD-L1 \geq 1% and <1% in the same study. CheckMate142 trial currently has multiple arms with Nivolumab combined with other agents.

Most commonly reported grade 3 or 4 adverse events in CheckMate142 study included elevated lipase (8%) elevated amylase (3%); and rest of grade 3 or 4 adverse events included fatigue (1%), diarrhea (1%), maculopapular rash (1%), increased alanine aminotransferase (1%), stomatitis (1%), abdominal pain (1%), increased creatinine (1%), decreased lymphocyte count (1%), colitis (1%), acute kidney injury (1%), adrenal insufficiency (1%), esophagitis (1%), increased gamma-glutamyltransferase (1%), gastritis (1%), pain (1%) No treatment related deaths were reported.

Please refer to the Investigator's Brochure for additional information for preclinical activity, toxicology and potential adverse effects.

4.2.2

Metformin in CRC:

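### Does the sample-size statement fail because it gives alpha 0.1 without a point null, only a historical response rate below 5%?

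*Combined protocol and SAP*

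**What the plan says.** The sample size is justified in two places, the Synopsis (Section 1, rationale for number of subjects) and Section 10.1, in almost the same words.

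- **Benchmark and target (10.1):** "Historically ORR with single agent Nivolumab in CRC is <5% and Metformin and Nivolumab combination will have ORR of 15" percent. The Synopsis has the same benchmark.
- **Method and error rates (10.1):** Simon's "MinMax two stage design is employed for the study with power of 80% and alpha of 0.1".
- **Interim rule (Synopsis, repeated in 10.1):** "If there is 1 response in first 18 patients in the first stage of the study", the trial goes on to 28 patients in total.
- **Success rule (10.1):** "If there are 3 or more responders out of the 28 patients then it would be positive study".

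Neither place gives a point null, and neither do the objectives in Section 3.

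The background bears on what a sensible null would be. Section 4.1 calls checkpoint inhibitors "ineffective in Microsatellite Stable (MSS) CRC". Section 4.2.1 reports two early nivolumab studies. In one, 1 of 14 colorectal patients responded, and "That patient had MSI-H positive CRC". In the other, "none of the 19 CRC patients had objective response", and those patients were mostly MSS.

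**The concern.** Type I error in a Simon design is defined at a single response rate. Here the reader gets an alpha and a range. The natural shortcut is to take the only number printed, 5%, as the null, and on that reading the rule exceeds its stated alpha by more than half (0.158 against 0.1).

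The primary conclusion is one count compared with a threshold of 3, so the null determines what a positive result rules out. If the null were 5%, a trial that just succeeds would carry a weaker claim than advertised. If the null was never recorded, someone could choose a convenient one after seeing the data. The planned two-sided 95% Clopper-Pearson interval (Section 10.2) does not settle it: at 3/28 it runs from 2.3% to 28.2% and includes 3%, 4% and 5%.

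**Working it through.** **Inputs, all from Section 10.1:** n1 = 18; continue with at least 1 response; N = 28; success with at least 3 responses; target 15%; alpha 0.1; power 80%. Alpha is taken as one-sided, as is usual for a Simon design. The null p0 is not given.

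**Formula.** Success requires at least 3 responses in 28 and at least 1 in the first 18. Hence

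P(success | p) = P[Bin(28, p) ≥ 3] − (1 − p)^18 × P[Bin(10, p) ≥ 3].

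The second term removes the cases in which all the responses would have fallen in the last 10 patients.

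**Step 1: the stated power.** At p = 0.15: 0.8129 − 0.0536 × 0.1798 = 0.8129 − 0.0096 = **0.803**. The stated 80% is reproduced.

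**Step 2: alpha as a function of the null.**

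| Null | P[Bin(28) ≥ 3] | (1 − p)^18 | P[Bin(10) ≥ 3] | Alpha |
|---|---|---|---|---|
| 3% | 0.0506 | 0.5780 | 0.0028 | 0.049 |
| 3.5% | 0.0733 | 0.5266 | 0.0043 | 0.071 |
| 4% | 0.0999 | 0.4796 | 0.0062 | 0.097 |
| 4.05% | 0.1027 | 0.4751 | 0.0064 | 0.0997 |
| 4.5% | 0.1298 | 0.4366 | 0.0086 | 0.126 |
| 5% | 0.1627 | 0.3972 | 0.0115 | 0.158 |

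Alpha crosses 0.10 at a null of 4.06%.

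**Step 3: which nulls give the printed design?** This is an exhaustive minimax search with target 15%, alpha at most 0.10 and power at least 0.80. Designs are written as r1/n1, r/N, where the trial continues or succeeds with more than r1 or r responses.

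| Null | Minimax design |
|---|---|
| 2.84% | 0/17, 1/19 |
| 2.85%, 3%, 3.5%, 4%, 4.05% | 0/18, 2/28 (the printed design) |
| 4.06% | 1/24, 2/28 |
| 4.1%, 4.5%, 4.9% | 0/20, 3/36 |
| 5% | 1/29, 4/44 |

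So the printed design comes out exactly for nulls of about 2.85% to 4.05%. A null of 5% would have required 44 patients.

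**Step 4: which results depend on the null?**

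- 0 to 2 responses: not positive, whatever the null.
- Exactly 3: the one-sided 90% Clopper-Pearson lower bound is 4.0% (4.06% by inverting the two-stage rule). This rejects 3% and 4% at one-sided 0.1, but not 5%.
- 4 or more: requiring at least 4 of 28 has alpha 0.049 at 5%, so 5% is rejected too.

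**Step 5: would a stricter threshold help?** Moving to 4 of 28 gives alpha 0.049 at 5%, but power at 15% falls from 0.803 to 0.620.

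**Step 6: the interim wording.** If continuation required exactly 1 response in 18, the chance of success at 15% would be P[Bin(18) = 1] × P[Bin(10) ≥ 2] = 0.078. That cannot be meant. Reading it as at least 1 gives the 80% power.

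**The case for a change.** The strongest case for a change is that the null is recovered only by working backwards, and only as a range. A null of 3% and one of 4% both lead to 18/28, yet the attained alpha is 0.049 in one case and 0.097 in the other. The background does not settle it: 0 of 19 has a one-sided 95% upper limit of 1 − 0.05^(1/19) = 14.6%. Section 10.2 does call its summary analyses hypothesis generating, but Section 10.1 still sets a formal rule and declares a positive study, so the error rate should be tied to a stated hypothesis. One sentence in two places would do it.

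Much of that is right. The null is not printed, and printing it with its exact alpha would be better reporting. What does not stand is the step from an unreported input to an alpha that fails. The benchmark sentence describes past results. It does not define the null as every rate up to 5%, and it does not promise alpha 0.1 across that range. The ambiguity between 3% and 4% also matters little for the claim, because whichever was entered, the printed rule rejects any rate up to 4.06% at one-sided 0.1. The 95% interval is stricter than a one-sided 0.1 test, so it is bound to be wide at the minimum success count; the plan does not offer it as a substitute for the null.

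**Conclusion.** The concern does not call for a change. The stated method, alpha, power, target, stage sizes and threshold agree with one another for any null from about 2.85% to 4.05%. That range lies inside the printed benchmark and fits a background describing essentially no activity in MSS disease. The figures of 0.126 at 4.5% and 0.158 at 5% are correct, but they count against the plan only if 4.5% or 5% was the null, and the stated method would then have produced 36 or 44 patients.

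The gap is one unreported input and one loosely worded interim rule. An analyst would read the interim rule as at least 1 response and would tie a positive result to a null of about 3% to 4%. The practical effect is confined to a result of exactly 3 of 28, which supports a claim against rates up to about 4% at one-sided 0.1 and not against 5%; a report of that result should say so. Raising the threshold would cost 18 percentage points of power (0.803 to 0.620).

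This rests on three assumptions: alpha is one-sided, the interim rule means at least 1 response, and the design came from a standard minimax search as stated.

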10.2 Statistical and Analytical Plans

Summary statistics will be presented for all safety, efficacy and biomarker parameter analyses. The purpose of these analyses is hypothesis generating. Various exploratory statistical tests may be applied to data generated from this trial to generate hypotheses to be tested in subsequent trials. In general, data for continuous parameters will be presented using descriptive statistics including sample size, mean, and median; standard deviation; and minimum and maximum. Categorical parameters be displayed using counts and percentages. Toxicities will be presented as worst toxicity per patient and will be reported as percent toxicity.

Objective response rate will be calculated as proportion (Responders/Total patients) along with 95% confidence intervals using the Clopper-Pearson method. Chi-square test or Fisher's exact test will be used to compare the efficacy in term of response rate, biochemical response (CEA) between the different groups stratified by biomarkers or other factors, respectively. Logistics regression

model will be further employed to test the adjusted effect of biomarkers on the response rate after adjusting for other clinical factors and demographic factors.

For progression free survival, progression or death from any cause will be defined as the event. Patients will be censored at time of last follow-up. For overall survival, death from any cause will be defined as the event. Patients will be censored at time of last follow-up. Overall survival (OS) and progression free survival (PFS) rates of two patient groups stratified by response or other factors will be estimated with the Kaplan-Meier method and compared between different groups using the log-rank test, respectively. The PFS and OS of each patient group at specific time points, such as 6 months, 1 year, 3 year, and 5 year, etc. will be also estimated alone with 95% CI. Cox proportional hazards models will be further used in the multivariable analyses to assess adjusted effect of response on the patients' OS and PFS after adjusting for other factors. Interaction terms between these factors will also be tested for statistical significance. The proportional hazards assumption will be evaluated graphically and analytically with regression diagnostics. Violations of the proportional hazards assumptions will be addressed by use of time-dependent covariates or extended Cox regression models.

For the biomarker study, descriptive statistics will be first used to summarize biomarker endpoints, including analyses of tumor biopsies. Biomarker data will also be displayed graphically, where appropriate. Depending on whether data is normally distributed, t-test or Wilcoxon rank sum test will be used to compare each biomarker between any two groups stratified by response or other factors, respectively. General linear model (GLM) will be used to compare each biomarker between responders and nonresponders with and without adjusting for other factors. Logistics regression model will be further employed to test the adjusted effect of biomarker on the response rate after adjusting for other factors.

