3.2 Secondary Objectives and Hypotheses

1. **Objective:** To determine the effect of nivolumab and Metformin combination on clinical outcomes, progression free survival and overall survival, and biochemical response (CEA).

Hypothesis: Metformin plus nivolumab will affect overall response rate, progression free survival, overall survival.

2. **Objective:** To compare the effect of nivolumab and metformin combination on immune and metabolic biomarkers in the tumor microenvironment and systemic circulation (pre and post treatment paired biopsies required).

Hypothesis: Metformin plus nivolumab will change the immune profile in the peripheral blood as well as the tumor microenvironment.

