 - Chemistry sodium, potassium, chloride, bicarbonate, magnesium, calcium, phosphorus, blood urea nitrogen, creatinine, glucose (random), total bilirubin, LDH, total protein, ALP, ALT, AST, and albumin
 - Tumor marker – CEA (every 2 cycles after cycle 2)
 - T3, FT4, TSH at cycle 2 and then after every 3 cycles
- Metformin and Nivolumab combination
- Cross sectional imaging (CT or MRI) for restaging at the end of C#2 (\pm 3 days), then repeat every 2 cycles (every 8 weeks)

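### CEA change has no planned estimate for the cohort: the only inferential method section 10.2 names for CEA is a subgroup chi-square or Fisher test of an undefined biochemical response

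*Combined protocol and SAP*

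**What the plan says.** Section 3.2 sets the secondary objective: "To determine the effect of nivolumab and Metformin combination on clinical outcomes, progression free survival and overall survival, and biochemical response (CEA"). The synopsis repeats CEA as a secondary endpoint, and section 10.1 lists it among the clinical endpoints that the sample size should allow to be evaluated.

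The method is in section 10.2, where chi-square or Fisher's exact test is to "compare the efficacy in term of response rate, biochemical response (CEA) between the different groups stratified by biomarkers or other factors". These tests need a categorical CEA variable. Neither that section nor any other gives a cut-off, a baseline value or an assessment time for biochemical response.

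Other text in section 10.2 bears on CEA indirectly. Continuous parameters are to be summarised by n, mean, median, SD and range. The analyses are called hypothesis generating, and further exploratory tests are allowed. A later paragraph on the biomarker study names the t-test, Wilcoxon test and a general linear model. The Clopper-Pearson interval is specified for objective response only.

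CEA is drawn repeatedly. Section 8.1.5.7, for example, lists "Tumor marker – CEA (every 2 cycles after cycle 2").

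**The concern.** CEA is a continuous value with a pre-treatment draw and several on-treatment draws. The one inferential method named for it reduces those values to yes or no and compares exploratory subgroups. That leaves two gaps.

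- **The objective is not answered.** It concerns the effect of the combination on CEA in the treated cohort. A comparison between biomarker subgroups does not estimate this, and a mean with an SD is not an estimate of change with an interval.
- **The endpoint is undefined and coarse.** A cut-off chosen after the data are seen is open to selection, and a dichotomised value usually carries less information than the change itself.

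This matters because few RECIST responses are expected: 15% of 28 is about 4. CEA change is therefore one of the few graded measures of activity in the trial.

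**Working it through.** **1. The plan's own power figure.** It concerns objective response only. Section 10.1 states: "Simon's MinMax two stage design is employed for the study with power of 80% and alpha of 0.1". The trial continues with at least 1 response in 18 and is positive with at least 3 in 28. At a true rate of 15%:

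- P(at least 3 of 28) = 0.8129.
- Subtract P(0 of 18) × P(at least 3 of the last 10) = 0.0536 × 0.1798 = 0.0096.
- Power = 0.803, which reproduces the stated 80%.

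No power, precision or effect size is stated for CEA.

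**2. Inputs for CEA.** All are assumptions, because the documents give none: normally distributed log-CEA change; group difference d of 0.5, 0.8, 1.0 or 1.2 SD; 20-50% of all patients called responders; two-sided 5%; splits of 14 v 14 (for example, a biomarker median split) and 4 v 24 (about the responder v non-responder split at 15% ORR).

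**3. Method.**
- Continuous: two-sample t-test, noncentrality d / √(1/n1 + 1/n2), df = n1 + n2 − 2. For 14 v 14 and d = 1.0 this is 1/√(2/14) = 2.646 on 26 df, giving power 0.721.
- Dichotomised: set the cut so that the chosen share of all patients respond, then sum exact binomial probabilities over every table the test rejects. For 14 v 14, d = 1.0 and 30% responders, the group rates are 0.463 and 0.137. Power is 0.491 (uncorrected chi-square) or 0.344 (Fisher), a loss of 23 or 38 points.

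**4. Results** (ranges over 20-50% responders; loss in percentage points).

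| Split | d (SD) | t-test | Chi-square | Fisher | Loss, chi-square | Loss, Fisher |
|---|---|---|---|---|---|---|
| 14 v 14 | 0.5 | 0.25 | 0.14-0.17 | 0.07-0.09 | 8-11 | 15-18 |
| 14 v 14 | 0.8 | 0.53 | 0.27-0.35 | 0.15-0.24 | 18-26 | 30-38 |
| 14 v 14 | 1.0 | 0.72 | 0.39-0.51 | 0.24-0.37 | 21-34 | 35-49 |
| 14 v 14 | 1.2 | 0.86 | 0.50-0.66 | 0.33-0.53 | 20-36 | 34-54 |
| 4 v 24 | 0.5 | 0.15 | 0.12-0.16 | 0.05-0.09 | −1 to 3 | 6-10 |
| 4 v 24 | 0.8 | 0.30 | 0.21-0.29 | 0.09-0.18 | 1-9 | 12-21 |
| 4 v 24 | 1.0 | 0.43 | 0.28-0.39 | 0.13-0.26 | 4-15 | 17-30 |
| 4 v 24 | 1.2 | 0.57 | 0.36-0.51 | 0.18-0.36 | 7-21 | 21-39 |

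At 14 v 14 and 1.0 SD, Fisher and chi-square differ by 14-15 points on identical dichotomised data. That part is Fisher's conservatism and not the cost of cutting CEA.

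**5. The cohort question.** In all 28 patients, for a mean log change of 0.3, 0.5, 0.6 or 0.8 SD, a paired t-test has power 0.334, 0.723, 0.864 or 0.983. A sign test of any fall has 0.198, 0.488, 0.646 or 0.880. The loss is 10-24 points. The 95% CI half-width for mean log change is 2.052/√28 = 0.39 SD. The plan names neither test and no such interval.

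**6. CEA schedule, set side by side.**

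| Visit | Calendar (section 7) | Section 8.1.5 |
|---|---|---|
| Screening | blank | listed |
| Day -14 | listed | listed |
| Cycle 1 Day 1 | listed | not listed |
| Cycle 1 Day 15 | listed | listed |
| Cycle 2 | blank | listed |
| Later cycles | 3, 5, 7 | every 2 cycles after cycle 2 |

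Day -14 and Cycle 1 Day 15 are the two early visits on which both places agree.

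**The case against.** The strongest reply is that section 10.2 does more for CEA than one test. CEA is a continuous efficacy measure, so the promised summaries cover it, and the open clause on exploratory tests would permit a log-change analysis. The t-test, Wilcoxon and general linear model might also be said to apply. A reader might therefore infer too much by saying that CEA is analysed only as yes or no. That part of the reply stands: the chi-square or Fisher test is the only *named inferential* method, not the only treatment of CEA.

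The rest of the reply is weaker. The t-test and linear model paragraph is about the biomarker study, and the objectives list CEA apart from the immune and metabolic biomarkers. Even if it applied, it names no baseline adjustment and no repeated-measures model. A clause that tests may be applied pre-specifies nothing.

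Three further inferences should not be drawn.

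- **A fixed loss of 15 to 50 points.** The table shows that the loss depends on effect size, cut, split and choice of test.
- **Loss of planned power.** The trial is powered for ORR alone, and the CEA comparison is exploratory.
- **Patients with low baseline CEA counted as non-responders.** With no cut-off or denominator stated, this cannot be known; a definition could be limited to raised baseline CEA.

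A mixed model over all draws also has a real weakness: treatment ends at progression, so later CEA values are lost for a reason tied to outcome.

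**Conclusion.** The point holds as a gap in the secondary analysis. The named CEA test rests on an undefined endpoint, and no whole-cohort estimate of CEA change with an interval is planned, although the objective calls for one. Neither conclusion needs any assumption.

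The size of the power loss does need assumptions. For near-balanced groups, 0.8-1.2 SD and 20-50% responders it is about 18-36 points (chi-square) or 30-54 (Fisher, in part its own conservatism). At 0.5 SD and 14 v 14 the chi-square loss is 8-11 points. At 4 v 24 it is under 10 points up to 0.8 SD and can be nil or slightly negative, though it grows again for larger effects. The primary endpoint and its decision rule are unaffected. This is a worthwhile, inexpensive improvement to a hypothesis-generating analysis.

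**What to change.** In section 10.2:

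- Make change in log(CEA) from the Day -14 value the main CEA analysis. Report the geometric mean ratio to baseline with 95% CI for the whole cohort at one fixed early visit, for example Cycle 1 Day 15.
- Compare subgroups at that visit by ANCOVA, adjusting for log baseline CEA.
- Use a mixed model over later draws as supportive only, and state that draws end at progression.
- State a rule for values below the assay limit, and confirm that the Day -14 sample precedes the first metformin dose.
- Keep biochemical response as a descriptive count among patients with raised baseline CEA, with the cut-off, the time point and the meaning of raised fixed in advance.

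First reconcile the CEA draws between the calendar and section 8.1.5 (screening, Cycle 1 Day 1, Cycle 2 and later cycles).

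The cost is SAP wording, a schedule correction and one simple model, with no new samples. There are two drawbacks. A mean ratio is less familiar to clinicians than a response proportion, which remains as a count. Cycle 1 Day 15 also falls only about two weeks after the first nivolumab dose, so it shows early change. A later visit could be chosen once the schedule agrees, at the price of more missing values.
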